10.1.6 Data Quality Assurance

- All participant data relating to the study will be recorded on printed or electronic CRF unless transmitted to the sponsor or designee electronically (e.g., laboratory data). The investigator is responsible for verifying that data entries are accurate and correct by physically or electronically signing the CRF.
- The investigator must maintain accurate documentation (source data) that supports the information entered in the CRF.
- The investigator must permit study-related monitoring, audits, IRB/IEC review, and regulatory agency inspections and provide direct access to source data documents.
- Monitoring details describing strategy (e.g., risk-based initiatives in operations and quality such as Risk Management and Mitigation Strategies and Analytical Risk-Based Monitoring), methods, responsibilities and requirements, including handling of noncompliance issues and monitoring techniques (central, remote, or on-site monitoring) are provided in the Monitoring Plan.
- The sponsor or designee is responsible for the data management of this study including quality checking of the data.
- The sponsor assumes accountability for actions delegated to other individuals (e.g., Contract Research Organizations).
- Study monitors will perform ongoing source data verification to confirm that data entered into the CRF by authorized site personnel are accurate, complete, and verifiable from source documents; that the safety and rights of participants are being protected; and that the study is being conducted in accordance with the currently approved protocol and any other study agreements, ICH GCP, and all applicable regulatory requirements.
- Records and documents should be retained for the longer of the two periods prescribed below:
 - Records and documents, including signed ICFs, pertaining to the conduct of this study must be retained by the investigator for 15 years after study completion unless local regulations or institutional policies require a longer retention period. No records may be destroyed during the retention period without the written approval of the sponsor. No records may be transferred to another location or party without written notification to the sponsor.

10.1.7 Source Documents

- Source documents provide evidence for the existence of the participant and substantiate the integrity of the data collected. Source documents are filed at the investigator's site.
- Data reported on the CRF or entered in the eCRF that are transcribed from source documents must be consistent with the source documents or the discrepancies must be explained. The investigator may need to request previous medical records or transfer records, depending on the study. Also, current medical records must be available.
- Definition of what constitutes source data can be found in the monitoring plan.

10.1.8 Study and Site Closure

The sponsor designee reserves the right to close the study site or terminate the study at any time for any reason at the sole discretion of the sponsor. Study sites will be closed upon study

completion. A study site is considered closed when all required documents and study supplies have been collected and a study-site closure visit has been performed.

The investigator may initiate study-site closure at any time, provided there is reasonable cause and sufficient notice is given in advance of the intended termination.

Reasons for the early closure of a study site by the sponsor or investigator may include but are not limited to:

- Failure of the investigator to comply with the protocol, the requirements of the IRB/IEC or local health authorities, the sponsor's procedures, or GCP guidelines
- Inadequate recruitment of participants by the investigator
- Discontinuation of further study intervention development
- If risk-benefit ratio becomes unacceptable owing to, for example,
 - Safety findings from this study (e.g. SAEs)
 - Results of parallel clinical Bayer studies or emerging data from literature
 - Results of parallel animal studies (on e.g. toxicity, teratogenicity, carcinogenicity or reproduction toxicity).
- If the study conduct (e.g. recruitment rate; dropout rate; protocol compliance) does not suggest a proper completion of the trial within a reasonable time frame.
- strategic reasons (e.g. the clinical development of the drug is stopped)

The site is entitled to end its participation in the study if necessary due to medical or ethical reasons.

For any of the above closures, the following applies:

- Closures should occur only after consultation between involved parties. Final decision on the closure must be in writing.
- All affected institutions (e.g., IEC(s)/IRB(s); competent authority (ies); study center; head of study center) must be informed as applicable according to local law.
- All study materials (except documentation that has to remain stored at site) must be returned to the sponsor. The investigator will retain all other documents until notification is given by the sponsor for destruction.

In the event of a study closure, participants on treatment and those in post-study follow-up must be taken care of in an ethical manner.

10.1.9 Publication Policy

The sponsor adheres to Good Publication Practice and authorship established by the International Committee of Medical Journal Editors (ICMJE). A Publication Roles and Responsibilities letter will be sent from Datavision, a publication management platform, to all authors for acknowledgement for each publication related to this study. For reference, the content of the letter can be found below. These roles and responsibilities are aligned with the sponsor's corporate publication policy.

Publication Roles and Responsibilities Letter:

Bayer is committed to adhering to the prevailing standards for Good Publication Practice (GPP3) (Battisti et al. 2015) as well as the criteria for authorship established by the International Committee of Medical Journal Editors (ICMJE).

The purpose of this letter is to inform you about the roles and responsibilities of you, as an author, and Bayer, as sponsor:

Author Responsibilities

1. In accordance with the ICMJE authorship criteria, you must meet all of the following criteria to be considered an author of the publication:
 - a. Substantial contributions to the conception or design of the work; or the acquisition, analysis, or interpretation of data for the work; AND
 - b. Drafting the work or revising it critically for important intellectual content; AND
 - c. Final approval of the version to be published; AND
 - d. Agreement to be accountable for all aspects of the work in ensuring that questions related to the accuracy or integrity of any part of the work are appropriately investigated and resolved.

Authorship will be rescinded if you fail to meet all of the above requirements.

2. Contributors who do not meet the above criteria but who contributed to the publication, e.g., those who provided editorial assistance, writing support, statistical support, or study support, may be listed in the acknowledgements, with their permission.
3. You will develop publications which are accurate, objective and complete, in a timely and responsible manner.
4. You will comply with all applicable disclosure requirements, and will disclose any potential conflicts of interest.
5. You (and any other author) retain full editorial control over the content of the manuscript.
6. You (and any other author) accept full responsibility for final approval of the manuscript prior to submission.
7. You agree to comply with all applicable laws, regulations, industry codes and professional standards.
8. You represent that you have obtained all necessary approvals including from your institution or employer in connection with this publication.
9. You represent that you have not been debarred, disqualified, blacklisted or banned or to the best of your knowledge currently under investigations or threat of investigation by any regulatory authority for debarment, disqualification, blacklisting or any similar regulatory action in any jurisdiction anywhere in the world. During the term of this Agreement, you shall promptly notify Bayer should you become subject of such debarment, disqualification, blacklisting or banning proceeding.

Bayer Responsibilities

1. Bayer, upon request, will provide data, documents, and materials necessary for development of the manuscript/publication (under a standard confidentiality agreement).

2. Bayer may review the draft publication for scientific and medical accuracy. You (and any other author) will consider any comments made by Bayer in good faith, but may accept or reject revisions suggested by Bayer.

10.2 Appendix 2: Clinical Laboratory Tests

- The tests detailed in [Table 10–1](#) will be performed by the local laboratory.
- Protocol-specific requirements for inclusion or exclusion of participants are detailed in [Section 5](#) of the protocol.
- Additional tests may be performed at any time during the study as determined necessary by the investigator or required by local regulations.
- Pregnancy Testing: not applicable

Table 10–1 Protocol-Required Safety Laboratory Assessments

Laboratory Assessments	Parameters			
Hematology	Platelet count	RBC indices: MCV MCH % reticulocytes	WBC count with differential: Neutrophils Lymphocytes Monocytes Eosinophils Basophils	
	RBC count			
	Hemoglobin			
	Hematocrit			
Clinical Chemistry	BUN	Potassium	AST/SGOT	Total and direct bilirubin
	Creatinine	Sodium	ALT/SGPT	Total protein
	Glucose (non-fasting)	Calcium	Alkaline phosphatase	
Routine urinalysis	
 • Specific gravity • pH, glucose, protein, blood, ketones, by dipstick • Microscopic examination (if blood or protein is abnormal) 			
Other screening tests	
 • Testosterone • PSA • TSH 
The results of each test must be entered into the CRF.
			

ALT = alanine aminotransferase; AST = aspartate aminotransferase; BUN = blood urea nitrogen; CRF = case report form; MCV = mean corpuscular volume; MCH = mean corpuscular hemoglobin; PSA = prostate-specific antigen; RBC = red blood cell; SGOT = serum glutamic-oxaloacetic transaminase; SGPT = serum glutamic-pyruvic transaminase; TSH = thyroid-stimulating hormone; WBC = white blood cell

Investigators must document their review of each laboratory safety report.

10.3 Appendix 3: Adverse Events: Definitions and Procedures for Recording, Evaluating, Follow-up, and Reporting

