8.2 Safety Assessments

Planned time points for all safety assessments are provided in the SoA in Section 1.3.

Safety assessments in this study are AEs, as recorded by the investigator. Descriptive summary tables will be presented for all safety parameters by each treatment arm.

All AEs will be coded using the Medical Dictionary for Regulatory Activities (MedDRA) coding system and graded using NCI-CTCAE version 5.0. A TEAE is defined as any event arising or worsening after start of study drug administration until 30 days after the last study drug intake.

Fatigue, cognitive function and depression will be assessed as described below.

Other AEs of interest including fractures, falls, fractures, and hypothyroidism will be collected with specific questions on CRF.

Study assessments for physical ability and cognitive function are described in [Table 8–1](#).

Table 8–1: Study Assessments for Physical Ability and Cognitive Function

Test	Description	Possible range of score	MCID / RCI from baseline
Physical ability tests			
Timed Up & Go (TUG)	The TUG test is used to assess a person's mobility and requires both static and dynamic balance. It uses the time that a person takes to rise from a chair, walk three meters, turn around, walk back to the chair, and sit down. Where possible, TUG time is to be measured by independent blinded assessors.	>1second	1 second (Davies et al. 2016)
Short Physical Performance Battery (SPPB)	The SPPB is a group of measures that combines the results of the gait speed, chair stand and balance tests.	0–12 points	0.5 points (Davies et al. 2016)
Cognitive Tests			
Hopkins Verbal Learning Test-Revised Total Recall (HVLTR TR)	The HVLTR is a learning and memory test, in which the participant is asked to learn and recall a list of 12 words over 3 trials.	0–36 words	±5 words (Wefel et al. 2011)
Hopkins Verbal Learning Test-Revised Delayed Recall (HVLTR DR)	Spontaneous recall is assessed before and after a delay.	0–12 words	±3 words (Wefel et al. 2011)
Hopkins Verbal Learning Test-Revised Delayed Recognition (HVLTR RECOG)	Recognition discriminability is also assessed after a delay. Four alternate versions of the test are used to minimize practice effects over time.	-12–+12 words	±2 words (Wefel et al. 2011)

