8.2.3 Clinical Safety Laboratory Assessments

The laboratory safety assessments will be performed at the time points outlined in the SoA (Section 1.3).

Laboratory values will be classified by NCI-CTCAE severity grade.

Additional or repeated laboratory safety assessments may also be obtained according to the investigator’s judgment.

- See Appendix 2 (Section 10.2) for the list of clinical laboratory tests to be performed and to the SoA (Section 1.3) for the timing and frequency.
 - The investigator must review the laboratory report, document this review, and record any clinically relevant changes occurring during the study in the AE section of the CRF. The laboratory reports must be filed with the source documents. Clinically significant abnormal laboratory findings are those which are not associated with the underlying disease, unless judged by the investigator to be more severe than expected for the participant's condition.
- If laboratory values from non-protocol specified laboratory assessments performed at the institution’s local laboratory are considered clinically significant by the investigator, then these also need to be reported as SAE or AE.
- All laboratory tests with values considered clinically significantly abnormal during participation in the study or within 28 days after the last dose of study intervention should be repeated until the values return to normal or baseline or are no longer considered clinically significant by the investigator or medical monitor.
 - If such values do not return to normal/baseline within a period of time judged reasonable by the investigator, the etiology should be identified and the sponsor notified.

- All protocol-required laboratory assessments, as defined in Appendix 2 (Section 10.2), must be conducted in accordance with the laboratory manual and the SoA (Section 1.3).
- If laboratory values from non-protocol specified laboratory assessments performed at the institution's local laboratory require a change in participant management or are considered clinically significant by the investigator (e.g., SAE or AE or dose modification), then the results must be recorded in the CRF.

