	
  
 Test	Reliable Change Index threshold (from baseline)	
   
 Hopkins Verbal Learning Test - Revised Total Recall (HVLTR TR)	±5 words	
 
 Hopkins Verbal Learning Test - Revised Delayed Recall (HVLTR DR)	±3 words	
 
 Hopkins Verbal Learning Test - Revised Delayed Recognition (HVLTR RECOG)	±2 words	
 
 Trail Making Test: Part A (TMTA)	±12 seconds	
 
 Trail Making Test: Part B (TMTB)	±26 seconds	
 
 Controlled Oral Word Association (COWA)	±12 words	
  
 
 • The proportion of participants with a decline of >10 points from baseline in the FACT-Cog domain by 24 and 52 weeks will be summarized. 
Fatigue
 
 • The proportion of participants with an increase of at least 1 point in worst level of fatigue from baseline during the past 24 hours (item 3 of BFI) by 24 and 52 weeks will be summarized. • Similarly, the proportion of participants with an increase of at least 1 point in in fatigue interference from baseline during the past 24 hours (items 4A through F of BFI) by 24 and 52 weeks will be summarized. The proportion of participants with a decline and the 95% CIs will be summarized for each treatment arm. This rate will be compared between the two arms using Cochran-Mantel-Haenszel test adjusting for stratification factors as captured by IWRS. 
Depression
 
 • The proportion of participants with a worsening of scores by PHQ-9 during the 24 and 52 week period from baseline will be summarized. Worsening is defined as an increase of at least 1 point in worst level of depression from baseline by 24 weeks and 52 weeks. 
AE, Exposure, other
 
 • AEs, drug-related AEs, and SAEs will be summarized by MedDRA coding system and NCI-CTCAE version 5.0 worst grade. • AE of interest (fall, fracture, hypothyroidism) will be summarized descriptively. • Time to deterioration of KPS will be calculated as the time from randomization (or time from first dose for participants in the lead-in phase) to the first date the participant had a decline in KPS score of at least 10 points. Data will be summarized using the Kaplan-Meier method. • Treatment exposure of the study intervention, including time on treatment and dose reductions, will be summarized. 		Test	Reliable Change Index threshold (from baseline)	Hopkins Verbal Learning Test - Revised Total Recall (HVLTR TR)	±5 words	Hopkins Verbal Learning Test - Revised Delayed Recall (HVLTR DR)	±3 words	Hopkins Verbal Learning Test - Revised Delayed Recognition (HVLTR RECOG)	±2 words	Trail Making Test: Part A (TMTA)	±12 seconds	Trail Making Test: Part B (TMTB)	±26 seconds	Controlled Oral Word Association (COWA)	±12 words

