### **5.5.6 Laboratory Data**

Laboratory data are summarized by laboratory tests for the treatment period, defined as the time from first dose up to 30 days post last dose of treatment. Laboratory data are converted to SI units prior to summarization. All laboratory tests are provided in patient data listings. The listings indicate the normal ranges for each parameter. Each value, if appropriate, is classified as falling above (H), below (L), or within normal range and also graded using the CTCAE criteria.

The observed data and change from baseline are summarized at each of the laboratory timepoints, using descriptive statistics, for hematology, chemistry and urinalysis laboratory tests.

The changes from baseline to maximum CTCAE grade during treatment are summarized by frequency and percentage of patients using shift tables for every gradable hematology and chemistry tests. Maximum CTCAE Grade is defined as the highest CTCAE version 5.0 grade reported during the treatment period.

A listing of patients with grade 3 or 4 laboratory values during treatment period is also provided.

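### Hypothyroidism is a protocol adverse event of interest, but neither document specifies an on-treatment TSH, and the SAP gives TSH no by-arm summary

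*Protocol*

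**What the plan says.** Protocol 8.2 states: "Other AEs of interest including fractures, falls, fractures, and hypothyroidism will be collected with specific questions on CRF". Protocol 9.4.2 adds: "AE of interest (fall, fracture, hypothyroidism) will be summarized descriptively". The breakdown by arm comes from the general rule in Protocol 8.2: "Descriptive summary tables will be presented for all safety parameters by each treatment arm".

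TSH appears as a test in one place, Protocol Table 10-1 in Appendix 2. The table is titled "Protocol-Required Safety Laboratory Assessments". Within it, TSH shares a row with testosterone and PSA, and that row is labelled "Other screening tests". Protocol 8.2.3 says that the tests in Appendix 2 "must be conducted in accordance with the laboratory manual and the SoA". The laboratory manual is not among the documents reviewed.

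The full schedules are reproduced as SAP Tables 8-1 and 8-2. They have one general laboratory row, which is not itemised, and a separate PSA row. TSH has neither a row nor a footnote.

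SAP 5.5.6 summarises observed values and changes from baseline "using descriptive statistics, for hematology, chemistry and urinalysis laboratory tests". Its shift tables cover gradable hematology and chemistry tests. It also says that every laboratory test will appear in patient listings, with values marked as high, low or normal where appropriate.

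**The concern.** Falls and fractures can be reported by the participant. Hypothyroidism is usually established by a blood test, so how often it is found depends on how often the test is done. If no TSH is scheduled on treatment, thyroid change comes to light when an investigator who knows the treatment decides to test.

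Protocol 2.1 suggests that men on darolutamide may have less fatigue, and fatigue is a plausible prompt for testing. Testing could therefore differ between arms, although the documents do not say that it will. Two consequences need to be kept apart:

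- **Under-ascertainment**, which needs only that testing is sparse. A finding of few or no cases in either arm is then hard to interpret.
- **Bias between arms**, which needs detection to differ by arm. A difference in counts could then reflect testing rather than drug effect.

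If TSH is in fact drawn serially, ascertainment is sound, but the plan does not turn the data into a comparison.

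**Working it through.** The plan states no figure on this point that could be reproduced. The check is mainly textual.

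**Step 1. Scheduled laboratory visits.** In SAP Tables 8-1 and 8-2 the general laboratory row is marked at screening and Week 1 Day 1, then at Weeks 4, 12, 24, 38 and 52 and at end of treatment (Week 8 is blank). That is 5 + 1 = 6 post-baseline laboratory visits, before any active follow-up after Week 52. TSH is named at none of them.

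**Step 2. TSH against PSA.** Both sit in the same row of Table 10-1.

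| | PSA | TSH |
|---|---|---|
| Own row in the schedules | Yes | No |
| Named in a schedule footnote | Yes (footnotes a and j) | No |
| Analysis in the SAP | PSA response and time to PSA progression | None named |

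The schedule makes PSA serial; the row label in Table 10-1 does not. Nothing equivalent is said for TSH. This makes a single screening TSH the likelier reading. It does not prove it, because the general laboratory row or the laboratory manual could include TSH.

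**Step 3. Both readings followed through.**

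| Reading | On-treatment measurement | By-arm analysis in SAP 5.5.6 |
|---|---|---|
| Screening only | 0 of 6 visits; otherwise at the investigator's discretion | None |
| With every laboratory panel | 6 of 6 visits | None: TSH is outside the hematology, chemistry and urinalysis groups of Table 10-1, so it is only listed |

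Either way the plan has a gap, but not the same one.

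**Step 4. What incomplete detection does to the counts.** Expected recorded cases per arm = n × p × d, where n is men per arm, p the true incidence and d the probability that a case is detected. From the planned 120 randomised 1:1, n = 120 / 2 = 60. The documents give neither p nor d, so the values below are assumptions, with d equal in both arms. The chance of recording no case in an arm is (1 − p × d)^60.

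| Assumed p | Cases, d = 1 | Cases, d = 0.5 | P(no case), d = 1 | P(no case), d = 0.5 |
|---|---|---|---|---|
| 5% | 3.0 | 1.5 | 0.046 | 0.219 |
| 10% | 6.0 | 3.0 | 0.002 | 0.046 |
| 20% | 12.0 | 6.0 | <0.001 | 0.002 |

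For p = 5% and d = 0.5, 60 × 0.05 × 0.5 = 1.5, and (1 − 0.025)^60 = 0.219.

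With the same p in both arms, the expected ratio of recorded cases is the ratio of the two detection probabilities. If they are equal, the ratio is 1 and the only effect is under-counting. If they differ, the ratio departs from 1 with no true difference. The documents give no basis for putting a number on that departure.

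**The case against.** The strongest reply is that the documents do not show that TSH is measured only once. PSA carries the same row label and is plainly serial. Hematology and urinalysis have no schedule rows of their own either. The whole table is headed as required safety laboratory work, and Protocol 8.2.3 defers timing partly to a manual that is not available here. This stands: the sound finding is that on-treatment TSH is unspecified.

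A reader might also infer that detection of hypothyroidism depends wholly on for-cause testing. The documents do not support that. Protocol 8.2 says that "hypothyroidism will be collected with specific questions on CRF", the schedules show adverse events of interest reviewed continuously in both arms, and Protocol 8.3 has them followed up whatever the cause. Diagnosed cases would therefore be captured in both arms. A question on a form cannot make a biochemical diagnosis, however, so that part of the concern remains on the screening-only reading.

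Third, SAP 5.5.6 promises listings of all laboratory tests, so TSH would not vanish. That stands too, but a listing is not a comparison by arm.

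Finally, Protocol 2.2 links raised hypothyroidism to apalutamide, which is not a study drug, and reports low, similar rates for darolutamide and placebo. It says nothing on hypothyroidism with enzalutamide. The step from fatigue to unequal TSH testing is an inference. This limits the weight of the bias argument, not that of the missing specification.

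**Conclusion.** The point holds in a limited form. Neither document specifies an on-treatment TSH, and the SAP plans no by-visit summary or shift table for it. The figure of 0 of 6 visits applies only if TSH is drawn at screening alone, which is the likelier reading but unproven. On that reading, hypothyroidism counts may be too low, and comparison between arms is biased only if testing differs by arm. A reader might infer that an artificial difference between arms is to be expected; the documents do not support that, because they give no detection rates and equal testing leaves the ratio at 1.

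The issue is modest. Hypothyroidism is a descriptive secondary safety endpoint with no test or power claim, the between-arm question arises only if the randomized phase goes ahead, and the Timed Up and Go comparison is unaffected. It is still worth correcting because the cost is small.

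A related but separate inconsistency is that the list of adverse events of interest in SAP 5.5.3 omits hypothyroidism, while footnote c of the SAP schedules retains it. Restoring the term to the list would not settle when TSH is measured or how it is analysed.

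**What to change.** 1. **Protocol Table 10-1 and the schedules.** Reconcile them so that they state whether and when TSH is measured on treatment. Make ascertainment the same in both arms, using blood already drawn at scheduled laboratory visits.
2. **SAP 5.5.6.** Add TSH to the by-visit summaries, by arm, with a shift table from baseline (normal or abnormal) to the worst on-treatment category. The above, below or within normal range classification already planned for the listings can be used.
3. **If TSH is kept as screening-only.** Record every on-study TSH test with its date, and report the share of men tested per arm beside the hypothyroidism count, labelled as for-cause detection.

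Items 1 and 2 cost one added local-laboratory assay on existing draws, an entry in the table and schedule, and a sentence and a table in the SAP; no visit is added. The downside is a small assay cost and some subclinical abnormalities to review. Item 3 needs only a CRF field and one table row, but leaves the count as for-cause detection.
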